8.7.5. Creatine Phosphokinase (CPK) Elevation

A Grade 3 or higher elevation in CPK should result in a repeat assessment within 2-4 weeks to ensure the result is transient or due to exercise and will not require a change in study intervention. A history regarding use of drugs known to cause increase of CPK (such as statins) physical activity or exercise preceding the CPK evaluation should be obtained.

Grade 4 elevations in CPK should have a repeat assessment after the participant has abstained from exercise for >24 hours. For persistent Grade 4 CPK elevations that are considered possibly or probably related to the IP, IP should be discontinued and the participant withdrawn from the study. Any participant receiving at least one dose of CAB LA and/or RPV LA who discontinue IP / Withdraw will initiate treatment with HAART enter the LTFU Phase for 52 weeks of follow-up.

8.7.6. Lipase Elevations and Pancreatitis

Participants with asymptomatic Grade 1 or 2 elevations in lipase may be followed closely for the development of symptoms.

Participants with asymptomatic Grade ≥ 3 elevations in lipase that are considered possibly or probably related to IP should have IP interrupted until serum lipase returns to Grade ≤ 2 . The lipase assay should be repeated within 2 weeks of any Grade ≥ 3 result. Participants with persistence of Grade ≥ 3 lipase in the absence of other diagnoses or reoccurrence of lipase elevation (at Grade ≥ 2) following reintroduction of IP should permanently discontinue IP.

Participants with a confirmed diagnosis of clinical pancreatitis that is considered possibly or probably related to IP should have IP held. After complete resolution of the episode, participants may be re-challenged with IP after discussion with the Medical Monitor, only if the Investigator has compelling evidence that the event was not caused by IP. Upon re-challenge, lipase determinations should be performed every 2 weeks for at least 6 weeks after re-initiation of treatment. With any elevation of lipase of Grade ≥ 2 or any recurrence of symptoms, the participant should discontinue IP and be withdrawn from study.

Any participant receiving at least one dose of CAB LA and/or RPV LA who discontinue IP / Withdraw will initiate treatment with HAART and enter the LTFU Phase for 52 weeks of **follow up**.

Drug Restart Following Transient Resolving Liver Events Not Related to Study Drug

Approval by VSLC for drug restart can be considered where:

Liver chemistries have a clear underlying cause (e.g., biliary obstruction, hypotension, and liver chemistries have improved to normal or are within $1.5 \times$ baseline and ALT $< 3 \times$ ULN). Ethics Committee or IRB approval of drug restart must be obtained, as required.

If restart of drug is approved by VSLC in writing, the participant must be provided with a clear description of the possible benefits and risks of drug administration, including the possibility of recurrent, more severe liver injury or death.

The participant must also provide signed informed consent specifically for the restart. Documentation of informed consent must be recorded in the study chart.

Study drug must be administered at the dose specified by VSLC.

Participants approved by VSLC for restarting study drug must return to the clinic once a week for liver chemistry tests for a minimum of one month and thereafter for as long as clinically indicated and then laboratory monitoring may resume as per protocol. If protocol defined stopping criteria for liver chemistry elevations are met, study drug must be stopped.

Refer to Section 12.3, U.S. Department of Health and Human Services, National Institutes of Health, National Institute of Allergy and Infectious Diseases, Division of AIDS. Division of AIDS (DAIDS) Table for Grading the Severity of Adult and Pediatric Adverse Events, Version 2.1. [March 2017]. Available from: <https://rsc.tech-res.com/docs/default-source/safety/daids-ae-grading-table-mar2017.pdf>

Refer to Section 12.7, Appendix 7: Liver Safety – Study intervention Restart Guidelines for further details.

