7.1.1.3.2. Drug Restart Following Transient Resolving Liver Events Not Related to Study intervention

Restart refers to resuming study treatment following liver stopping events in which there is a clear underlying cause (other than DILI) of the liver event (e.g. biliary obstruction, pancreatic events, hypotension, acute viral hepatitis). Furthermore, there should be no evidence of alcoholic hepatitis or hypersensitivity, and the study treatment should not be associated with HLA markers of liver injury.

Approval by the VSLC for drug restart can be considered where:

- Investigator requests consideration for study treatment restart if Liver chemistries have a clear underlying cause (e.g., biliary obstruction, hypotension and liver chemistries have improved to normal or are within 1.5 x baseline and ALT <5xULN).
- Furthermore, there should be no evidence of fever, rash, eosinophilia, hypersensitivity, alcoholic hepatitis or possible study treatment-induced liver, and the drug should not be associated with HLA markers of liver injury. (If restart of TRIUMEQ or any other abacavir- containing product is being considered then the Subject must be HLA-B*5701 negative).
- Ethics Committee or Institutional Review Board approval of drug restart/rechallenge must be obtained, as required.
- If restart of drug is approved by the VSLC in writing, the subject must be provided with a clear description of the possible benefits and risks of drug administration, including the possibility of recurrent, more severe liver injury or death.
- The subject must also provide signed informed consent specifically for the restart. Documentation of informed consent must be recorded in the study chart.
- Study drug must be administered at the dose specified by the VSLC.
- Subjects approved by the VSLC for restarting IP must return to the clinic once a week for liver chemistry tests for a minimum of one month and thereafter for as

long as clinically indicated and then laboratory monitoring may resume as per protocol.

- If after study treatment re-start, subject meets protocol-defined liver chemistry stopping criteria, follow usual stopping criteria instructions..
- The Medical Monitor and the Ethics Committee or Institutional Review Board as required, must be informed of the subject's outcome following study treatment restart
- Any adverse events should be recorded on the appropriate eCRF(s), and reported where applicable, as per Section 8.5.

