12.7.3. VSLC Decision Process for Drug Restart Approval or Disapproval

- Principal Investigator (PI) requests consideration of drug re-initiation for a participant stable or improving on IP, who exhibits liver chemistry elevation meeting participant stopping criteria, which is transient, non-drug-related, and liver chemistries have improved to normal or are within 1.5x baseline and ALT < 5xULN.
- GSK Medical Monitor and GCSP Physician to review the participant's diagnosis restart risk factors (Hepatotoxicity Panel consultation is available) and complete checklist (Table 9).
 - *must present source data defining the participant's current resistance profile with documented evidence of extensive drug resistance and previous drug history.*
- The local operating company (LOC) medical director should be informed that study drug restart is under consideration and of the final decision, whether or not to proceed.
- Relevant physicians (listed below) must review and agree on action to be taken regarding request for drug restart:
- Safety Review Team Leader, Safety Development Leader, or Senior Safety Physician
- MDL and PPL
- Request is taken to VSLC for final decision

Table 9 Checklist for Phase IIb drug restart after well-explained liver injury (e.g. biliary, pancreatic, hypotensive events, congestive heart failure (CHF), acute viral hepatitis), and improvement of liver chemistry to normal or $\leq 1.5x$ baseline & ALT < 5xULN

	Yes	No
Is participant stable or improving on IP?		
Do not restart if the following risk factors at initial liver injury:		
fever, rash, eosinophilia, or hypersensitivity		
drug-induced liver injury		
alcoholic hepatitis (AST > ALT, typically < 10xULN)		
IP has an HLA genetic marker associated with liver injury (e.g. lapatinib, abacavir, amoxicillin/clavulanate)		
Source data defining the participant's current resistance profile		
Previous drug history		

Figure 5 VSLC process for drug restart approval or disapproval

12.7.4. Medical monitor, GCSP Physician and PI actions for Restart or Rechallenge following VSLC decision

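### The protocol gives two ALT ceilings for the same liver restart decision: below 3xULN in Section 8.7.6, below 5xULN in Section 7.1.1.3.2 and Appendix 7

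*Protocol*

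**What the plan says.** Three parts of the current protocol describe when the VSLC may consider approving a restart after a liver event that has another explanation.

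- **Section 7.1.1.3.2**, headed "Drug Restart Following Transient Resolving Liver Events Not Related to Study intervention", requires a clear underlying cause and that "liver chemistries have improved to normal or are within 1.5 x baseline and ALT <5xULN".
- **Appendix 7, Section 12.7.3**, the committee's decision process, has the investigator make the request once "liver chemistries have improved to normal or are within 1.5x baseline and ALT < 5xULN". The form to be completed is Table 9, "Checklist for Phase IIb drug restart after well-explained liver injury", and its title repeats the 5xULN ceiling.
- **Section 8.7.6**, on lipase and pancreatitis, ends with a separate block headed "Drug Restart Following Transient Resolving Liver Events Not Related to Study Drug". The condition there opens "Liver chemistries have a clear underlying cause (e.g., biliary obstruction, hypotension, and liver chemistries have improved to normal or are within", and with its figures the second half reads "liver chemistries have improved to normal or are within $1.5 \times$ baseline and ALT $< 3 \times$ ULN". The block closes by sending the reader to Appendix 7 for more detail.

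Section 8.7.1, which deals with liver chemistry within 8.7, contains no restart criterion.

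**The concern.** The headings in 7.1.1.3.2 and 8.7.6 describe the same situation, the decision-maker is the same committee, and the wording is almost the same apart from the ALT figure. An investigator who reads 8.7.6 would conclude that a participant with ALT between 3 and 5xULN cannot be put forward. One who reads 7.1.1.3.2 could conclude the opposite.

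The decision is to re-expose a participant after a liver stopping event. Both main-body versions require specific consent that warns of recurrent, more severe liver injury or death. For participants on injections, Section 6.8.1 says that both long-acting drugs may remain measurable for more than a year, so a restart by injection cannot be quickly undone. A condition for entering that process should have one value.

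The 8.7.6 block also looks like a copy that was not kept in step. It sits under an unrelated heading. It also lacks the conditions in 7.1.1.3.2 on fever, rash, eosinophilia, hypersensitivity, alcoholic hepatitis and HLA markers.

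**Working it through.** There is no planned statistic to reproduce. The check compares the texts and then works out where the two ceilings give different answers.

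**Side by side**

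| Place | Cause of event | Baseline condition | ALT ceiling |
|---|---|---|---|
| 7.1.1.3.2 | clear, not study drug | normal or within 1.5x baseline | <5xULN |
| 12.7.3, process text | not drug-related | normal or within 1.5x baseline | <5xULN |
| Table 9, title | well explained | normal or at most 1.5x baseline | <5xULN |
| 8.7.6, restart block | clear, not study drug | normal or within 1.5x baseline | <3xULN |

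The first two conditions agree in substance in all four places. Only the ceiling differs.

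**Where the answer changes**

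1. Below 3xULN both ceilings are met. At 5xULN or above neither is. They can disagree only for ALT from 3 to <5xULN.
2. ALT of 3xULN or more is not normal, so the participant must qualify through the baseline route. This holds whether the ceiling is read as attached to both routes or only to the baseline route.
3. Take that route to mean ALT no higher than 1.5 times baseline ALT, as the Table 9 title suggests. With baseline ALT written as b x ULN, the conflict requires 3 ≤ ALT/ULN ≤ 1.5b and ALT/ULN < 5.
4. The range is empty unless 1.5b ≥ 3, that is b ≥ 3/1.5 = 2. It covers the whole span up to 5xULN once b ≥ 5/1.5 = 3.33.

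| Baseline ALT (xULN) | 1.5 x baseline (xULN) | ALT range in conflict (xULN) |
|---|---|---|
| below 2 | below 3 | none; fails every version at 3 or above |
| 2.0 | 3.0 | 3.0 only |
| 2.5 | 3.75 | 3.0 to 3.75 |
| 3.0 | 4.5 | 3.0 to 4.5 |
| 3.33 or more | 5.0 or more | 3.0 to <5.0 |

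**Can such participants be in the study?** Yes. Exclusion criterion 23 bars ALT of 5xULN or more, or of 3xULN or more with raised bilirubin, over the last 6 months in LATTE. A baseline ALT of 2xULN is not excluded by it. Criterion 11 allows hepatitis C co-infection under conditions, and the stopping criteria in 7.1.1 have a branch for baseline ALT above ULN. The documents do not say how many participants have such a baseline.

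**The case against.** The best case on the other side is that the process protects the participant whichever figure is read. Under either version approval may only be considered. Restart also needs written VSLC approval, ethics approval where required, specific consent, and weekly liver tests for at least a month. The committee's own process and checklist carry one figure, and 8.7.6 refers to that appendix. Much of this stands. Meeting a threshold does not by itself permit restart, and the VSLC is not handed a checklist with two thresholds. A reader might infer that the committee would be applying two criteria, but Appendix 7 does not support that. The ambiguity falls mainly on the investigator, who starts the request, and on an ethics reader who meets 8.7.6. A pointer for further detail is not a rule of precedence, and here it leads to the other number.

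Two other stronger readings are tempting:

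- **Every request with ALT from 3 to <5xULN is affected.** The shared baseline condition rules this out. On the reading used above, participants with baseline ALT below 2xULN fail every version in that range.
- **Every such case concerns a long-acting injection.** The restart text speaks of study drug or study treatment in general, and Section 7.1 counts oral DTG + RPV as investigational product.

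Nor can the intended value be inferred from the larger number of places that say 5xULN. Counting copies does not show which one the sponsor meant.

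**Conclusion.** The protocol contradicts itself on the ALT ceiling for considering a restart, in current text and with no statement of which version governs. The disagreement matters for ALT from 3 to <5xULN in participants with baseline ALT of about 2xULN or more. This rests on reading the baseline condition as ALT no higher than 1.5 times baseline ALT.

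The affected group also needs to have had a liver stopping event with a clear cause other than study drug, in a study of about 100 participants. Few cases are expected, possibly none, and the documents give no figure from which to estimate the number. The primary endpoint, the sample size and the stopping criteria are untouched. The point still deserves correction, because an investigator could reach opposite answers on re-exposure depending on the section read.

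**What to change.** The sponsor should decide which restart criterion it intends and state it identically in 7.1.1.3.2, 8.7.6 (if any restart text stays in the main toxicity section), 12.7.3 and Table 9. Liver restart text that is kept should move out of the lipase and pancreatitis section, and its accompanying conditions should be aligned with 7.1.1.3.2 at the same time. Simply deleting the 8.7.6 block would settle the threshold by default, so the sponsor's decision should come first. This review takes no position on the value.

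The cost is a short text change. Appendix 2 (12.2.1) requires IRB/IEC approval of amendments before changes are implemented, so it is not entirely free, but it can be bundled with other corrections.

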8.7.7. Decline in Renal Function

Participants who experience an increase in serum creatinine from Baseline of 45 micromoles/liter ($\mu\text{Mol/L}$) (or 0.5 milligrams/deciliter [mg/dL]) should return for a confirmatory assessment within 2 to 4 weeks. A urinalysis and urine albumin/creatinine and urine total protein/albumin ratios should also be done at this confirmatory visit. If the creatinine increase is confirmed, the investigator should contact the study medical monitor to discuss additional follow-up and medical management.

Participants who have a decline in the estimated GFR (using the CKD-EPI method) of $>50\%$ from Baseline must return for a confirmatory assessment as soon as possible [Levey, 2009]. A urinalysis and urine albumin/creatinine and urine protein/creatinine ratios should also be done at this confirmatory visit. If the estimated GFR has declined by $>50\%$ (confirmed), then study drug should be withheld and the investigator should contact the study medical monitor to discuss the rationale for restarting study drugs (if appropriate). Consideration for confounding factors (e.g., background therapy, other medications, dehydration, concurrent conditions) should be taken into account, and a nephrology consult may be obtained.

8.7.7.1. Proximal Renal Tubule Dysfunctions (PRTD)

PRTD is defined as:

Confirmed rise in serum creatinine of $\geq 0.5 \text{ mg/dL}$ from Baseline AND serum phosphate $< 2.0 \text{ mg/dL}$;

Either of the above accompanied by any two of the following:

- Glycosuria (≥ 250 mg/dL) in a non-diabetic;
- Low serum potassium (< 3 mEq/L);
- Low serum bicarbonate (< 19 mEq/L).

Participants meeting criteria for PRTD must return for a confirmatory assessment within 2 weeks of diagnosis. A urinalysis should also be performed at the time of the confirmatory assessment. If PRTD is confirmed participants should have study drug withheld and the investigator should contact the Study medical monitor to discuss the rationale for restarting study drugs (if appropriate). Consideration for confounding factors (e.g., NRTI backbone, other medications, dehydration, concurrent conditions) should be taken into account, and a nephrology consult may be obtained. If study drug is reinitiated, it should have been withheld for no more than 4 weeks.

8.7.7.2. Proteinuria

Participants with an abnormal urine microalbumin/creatinine ratio (> 0.3 mg/mg, > 300 mg/g, or > 34 mg/mmol) that represents a change from Baseline and no associated increase in creatinine, should have a repeat spot urine microalbumin/creatinine ratio performed within 2-4 weeks. If confirmed, then consideration should be given to additional evaluation after consultation with the study medical monitor. Additional evaluation may include a 24-hour urine protein and creatinine measurement and nephrology referral.

Participants with an abnormal urine albumin/creatinine ratio (> 0.3 mg/mg, 300 mg/g, or > 34 mg/mmol and representing a change from Baseline) and a serum creatinine increase > 45 μ mol/L (or 0.5 mg/dL) should have confirmation of both results within 2 weeks. If confirmed, the study medical monitor should be contacted immediately. Agreement on further management should be agreed between the investigator and medical monitor.

8.7.8. QTc Prolongation

Participants with an average QTc interval > 550 msec from three or more tracings separated by at least 5 minutes should have IP discontinued. These criteria are based on an average QTc value of triplicate ECGs. If an ECG demonstrates a prolonged QT interval, obtain 2 more ECGs over a brief period (~ 5 -10 minutes) and use the averaged QTc values of the 3 ECGs to determine whether the participant should be discontinued from the study. If an alternative cause of the QT prolongation is determined (e.g., participant receiving drug known to cause prolonged QT or TdP), then IP may be restarted after consultation with, and agreement by, the Medical Monitor.

8.7.9. Injection Site Reactions (ISRs)

Injection site reactions will be managed through investigator assessment throughout the study. All ISRs that are either serious, Grade 3 or higher, or persisting beyond 2 weeks must be discussed with the Medical Monitor to determine etiology and assess appropriate continued study participation.

Digital photographs may be documented where possible on all participants who have an injection site reaction, with observable findings, that is either serious or Grade 3 or higher, or that persists beyond 2 weeks. Dermatology will be consulted on all participants who have an injection site reaction considered serious, Grade 3 or above, or if clinically significant and persistent beyond 30 days and others if the Investigator or Medical Monitor feels it is medically necessary.

Details regarding photo collection and any other follow up will be given by the Medical Monitor at the time of assessment.

ISR discomfort can be managed symptomatically (e.g., cold/warm compress, acetaminophen, ibuprofen) if the reaction is interfering with the participant's ability to perform activities of daily living. The required intervention should be documented on the appropriate eCRF page.

8.7.10. Allergic reaction

Participants may continue study drug for Grade 1 or 2 allergic reactions at the discretion of the Investigator. The participant should be advised to contact the Investigator immediately if there is any worsening of symptoms or if further systemic signs or symptoms develop. Antihistamines, topical corticosteroids, or antipruritic agents may be prescribed.

Participants with Grade ≥ 3 allergic reactions that are considered to be possibly or probably related to the study drug should permanently discontinue the CAB LA + RPV LA regimen and the participant should be withdrawn from the study. Participants should be treated as clinically appropriate and followed until resolution of the AE.

8.7.11. Abacavir Hypersensitivity Reaction (ABC HSR)

This section applies to participants who discontinue LA treatment and enter LTFU and are administered a regimen containing ABC.

The most significant toxicity associated with ABC is the well-characterized drug-related hypersensitivity reaction (HSR). A detailed clinical description of this reaction (including the type and severity of events that can occur on re-challenge or reintroduction following ABC interruption for non-HSR reasons) and guidance regarding its management are included in the Local Country Prescribing Information for EPZICOM. Investigators must familiarize themselves with this information on ABC HSR in the Local Country Prescribing Information for each of these products prior to initiating participants on ABC therapy.

Studies have shown that carriage of the *HLA-B*5701* allele is associated with a significantly increased risk of a HSR to ABC. In the prospective study CNA106030 (PREDICT-1), the use of pre-therapy screening for the presence of *HLA-B*5701* and subsequently avoiding ABC in *HLA-B*5701* positive participants, significantly reduced the incidence of clinically suspected ABC HSR from 7.8% (66 of 847) to 3.4% (27 of 803) ($p < 0.0001$). In clinical studies EPZ108859 (ARIES) and CNA109586 (ASSERT),

0.8% (4/515) and 3.1% (6/192) of participants who were *HLA-B*5701* negative and who received ABC developed a clinically suspected ABC HSR, respectively.

In any participant treated with ABC, the clinical diagnosis of suspected HSR (as detailed in the Local Country Prescribing Information) must remain the basis of clinical decision making. Regardless of *HLA-B*5701* status, it is important to permanently discontinue ABC and not re-challenge with ABC (i.e., ZIAGEN, EPZICOM/KIVEXA, TRIZIVIR, or TRIUMEQ) if a HSR cannot be ruled out on clinical grounds, due to the potential for a severe or even fatal reaction.

